**A Mechanistic Perspective on Post-Activation Performance
Enhancement Responsiveness: A Randomized Controlled
Study of Acute Changes in Muscle Architecture, Contractile
Property Kinetics, and Muscle Excitability**

NCT06982937

18.05.2025

Objectives and endpoints.

The primary objective is to test whether a heavy conditioning activity (CA; one set of 2–3 repetitions at ~90% 1RM) produces post-activation performance enhancement (PAPE) in countermovement jump (CMJ) height compared with a control treadmill warm-up within the 4–12 min window after the intervention. The analysis does not assume *a priori* when the maximal effect occurs; instead, the minute of maximal between-group difference (denoted T^*) will be identified empirically. The primary endpoint is the change in CMJ height from baseline (ΔCMJ) at post-intervention time points (4, 6, 8, 10, 12 min). Secondary endpoints include the time-course of ΔCMJ within the experimental group (EXP), individual responder status at each time point, and the associations between neuromuscular phenotype—estimated as %MHC-I from tensiomyography (TMG)—and the magnitude, timing, and likelihood of response. Ultrasound (USG) morphology (muscle thickness, pennation angle, derived fascicle length) will be analysed in parallel to performance endpoints. Electromyography (EMG), where available, will be treated analogously to USG/TMG (see below).

Data handling and derived variables.

At each time point, CMJ height is the mean of three trials; ΔCMJ and percentage change (% ΔCMJ) will be computed relative to baseline. Individual response is classified using MDC. USG outcomes will be averaged across three images; fascicle length is calculated as thickness divided by the sine of pennation angle (degrees converted to radians). TMG-based %MHC-I is estimated from delay, contraction, and half-relaxation times using the published multivariable model; TMG amplitudes and time constants may also be expressed as Δ or % Δ . If EMG is collected, signals will be band-pass filtered, rectified, quantified with 50-ms RMS, normalized (to MVC or M-wave), and summarized over task-relevant phases; % Δ at 4–12 min is computed analogously. Values >3.5 SD from group-time means will be flagged; primary analyses include all data, with winsorized sensitivity checks reported only if inferences change. Missing data will be not imputed for the primary analysis; mixed-effects models accommodate missingness assuming MAR.

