Primary analysis and identification of the peak time (T^*).

The confirmatory analysis uses a RM-ANOVA with ΔCMJ as the outcome, Group (EXP vs CON), Time (time effect: 4, 6, 8, 10, 12 min), and Group \times Time. If the interaction is significant, we estimate adjusted between-group contrasts at each minute with Bonferroni correction across the five time points. T^* is defined as the minute showing the largest positive EXP–CON difference in estimated marginal means (EMMs) with the smallest p-value. We report the EMM difference at T^* (95% CI) and effect size (d’Cohen). Greenhouse–Geisser correction if needed.

Within-group time-course and kinetics.

To describe the temporal profile without prespecifying a target minute, we analyse ΔCMJ across time within EXP using a one-way repeated-measures ANOVA (or LMM if assumptions are violated), followed by Bonferroni-adjusted pairwise EMMs to locate the within-group peak. To characterise response timing at the individual level, we model time to first and time to peak response (4–12 min) using Kaplan–Meier curves with censoring at 12 min, compare strata by log-rank tests, and fit Cox proportional-hazards models to estimate hazard ratios (HR, 95% CI) and concordance (C-index). This kinetics framework provides an assumption-light estimate of when athletes typically express PAPE.

Responder analyses and discrimination.

Responder distributions (Positive/neutral/adverse) will be compared between EXP and CON at each minute using likelihood χ^2 test. For mechanistic discrimination at specific minutes (including T^* once identified), we fit logistic models with %MHC-I as a continuous predictor and report ORs (95% CI),

Nagelkerke R², AIC, Hosmer–Lemeshow calibration, and ROC-AUC with sensitivity, specificity, and Youden's J cut-offs. Moderation analysis also will be used with simple slope analysis.

Phenotype and morphology linkages (USG/TMG/EMG).

Associations between %MHC-I and Δ CMJ will be quantified at each minute using Pearson's r. USG variables (thickness, pennation angle, fascicle length) will be analysed with the same three lenses applied to performance: (i) within-EXP time-course (rmANOVA/LMM with Tukey), (ii) responder linkage at each minute (one-way ANOVA or robust alternative; Hedges' g for P vs X), and (iii) phenotype linkage (correlations and moderation models). TMG (e.g., Dm, Tc, Tr) and EMG (e.g., normalized RMS, median frequency) follow this identical framework to ensure coherence across modalities.

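### The time-to-first-response curve is read as the onset of PAPE, but no EXP-versus-CON comparison of the curves is specified, and taking the first of five MDC crossings raises the chance response rate.

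*Combined protocol and SAP*

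**What the plan says.** The objectives define the PAPE question as CMJ height after the conditioning activity "compared with a control treadmill warm-up within the 4–12 min window after the intervention".

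The section *Data handling and derived variables* sets out the measurement: "At each time point, CMJ height is the mean of three trials; ΔCMJ and percentage change (% ΔCMJ) will be computed relative to baseline". The next sentence reads "Individual response is classified using MDC". It gives no confidence level or source for the MDC, and does not say whether it refers to single trials or to three-trial means.

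The section "Within-group time-course and kinetics" opens with a repeated-measures ANOVA limited to EXP. For individual timing it then says "we model time to first and time to peak response (4–12 min) using Kaplan–Meier curves with censoring at 12 min", and goes on to "compare strata by log-rank tests, and fit Cox proportional-hazards models to estimate hazard ratios (HR, 95% CI) and concordance (C-index". The Kaplan–Meier sentence names no group, and strata is not defined anywhere. The section closes: "This kinetics framework provides an assumption-light estimate of when athletes typically express PAPE".

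Two controlled analyses stand elsewhere. T* is the minute of the largest EXP–CON difference, and responder distributions are compared between EXP and CON at each minute. The multiplicity paragraph covers the five between-group contrasts and the correlation families. It names nothing for repeated MDC crossings.

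**The concern.** An MDC bounds the measurement error of one baseline-to-retest comparison. Time to first response applies it at five minutes and counts the first crossing as the event, so each athlete has five chances to be called a responder. Because all five changes subtract the same baseline, an athlete whose baseline was low by chance is favoured at every minute.

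A curve built this way mixes three things: true PAPE, chance crossings, and any change that would also have followed the control warm-up. Only the first is PAPE as the objectives define it. The control arm is what separates them, and the plan does not specify that it be used here. What is at stake is a named secondary question, the timing of response. Its Kaplan–Meier figures and hazard ratios will be reported, and the cumulative proportion on the EXP curve could be read as the share of athletes showing PAPE.

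**Working it through.** The plan gives no MDC value, sample size or expected response rate, so there is no figure of its own to reproduce. The check asks how often an athlete with no true change would be called a responder.

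**Inputs from the plan.** Five looks (4, 6, 8, 10 and 12 min); one shared baseline; three-trial means; response by MDC; first crossing as the event.

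**Assumptions.** Normal errors, equal and independent across sessions. MDC95 = 1.96 × SE of the difference, or MDC90 = 1.645 × SE of the difference. Only upward crossings count.

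**Correlation between looks.** With session error variance s², each change has variance 2s², and two changes share the baseline error s². The correlation is s²/2s² = 0.5.

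**One look.** P(Z > 1.96) = 2.5%; P(Z > 1.645) = 5.0%.

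**Any of five looks, if independent (upper reference).** 1 − 0.975⁵ = 11.9%; 1 − 0.95⁵ = 22.6%.

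**Any of five looks, shared baseline (correlation 0.5).** P(first crossing at look k) = ∫ φ(u) · A(u)^(k−1) · [1 − A(u)] du, where A(u) = Φ((c − √0.5·u)/√0.5) and c is 1.96 or 1.645.

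| First crossing at | 4 min | 6 min | 8 min | 10 min | 12 min | Any |
|---|---|---|---|---|---|---|
| MDC95 | 2.50% | 2.04% | 1.74% | 1.52% | 1.35% | 9.15% |
| MDC90 | 5.00% | 3.78% | 3.06% | 2.57% | 2.22% | 16.63% |

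A simulation of 1,000,000 athletes gave 9.11% and 16.56%. The text uses about 9.1% and 16.6%. That is a rise over one look of 9.1/2.5 = 3.6 times and 16.6/5.0 = 3.3 times.

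**Timing of chance events.** The share at 4 min is 2.50/9.15 = 27% (MDC95) or 5.00/16.63 = 30% (MDC90), against 20% if uniform. The 4 and 6 min looks together hold 4.54/9.15 = 50% or 8.78/16.63 = 53%, against 40%. In the same simulation the minute of the largest change was uniform, at 20% each, so time to peak has no early lean when there is no true change.

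**Shift common to both arms.** Replace c by c − shift, with the shift in SE of the difference.

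| Shift | −1 | −0.5 | 0 | +0.5 | +1 |
|---|---|---|---|---|---|
| MDC95, any of five | 0.7% | 2.9% | 9.1% | 22.5% | 43.2% |
| MDC90, any of five | 1.7% | 6.1% | 16.6% | 34.9% | 58.0% |

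**MDC basis.** If the MDC came from single trials and trial errors are independent, the threshold is √3 times larger on the three-trial scale: 1.96 × 1.732 = 3.39 or 1.645 × 1.732 = 2.85. With no shift, the any-of-five rate is then about 0.2% or 1.0%.

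**The case against.** The strongest objection is that a missing control curve is inferred, not stated. The restriction to EXP sits in the ANOVA sentence alone; the Kaplan–Meier sentence names no group, and the strata could be EXP and CON. This stands in part. A reader might conclude that the plan excludes CON from the curves, and the text does not say so. But the heading says within-group, the preceding sentence is confined to EXP, and the plan names both arms where it intends a group comparison. The firm defect is that strata is undefined and no group comparison of the curves is specified. Either reading needs the same edit.

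Second, the curve is not the plan's main answer on timing. T* is, and it is controlled, as are the per-minute responder tests. This stands, and it limits the weight of the point. Those analyses still do not yield a controlled cumulative first-response curve, because they treat each minute separately.

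Third, the size depends on what the plan leaves open. This also stands. The high end of the shift range is an assumption: the documents do not say whether baseline jumps follow a warm-up or whether EXP does one, and repeated jumping could lower performance as easily as raise it. The 0.2–1% result under a single-trial MDC shows that the chance component could be negligible.

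**Conclusion.** The point holds as a gap in a secondary analysis. An uncontrolled curve is not an estimate of when PAPE occurs when PAPE is defined against a control, and the plan specifies nothing to make this curve controlled. Taking the first of five crossings raises the chance response rate from 2.5% to about 9.1% (MDC95) or from 5% to 16.6% (MDC90). This assumes no true change, equal independent errors and an MDC matched to three-trial means. The rate is about 0.2–1% if a single-trial MDC is applied to the means. With a matched MDC, a common shift of −1 to +1 SE of the difference spans 0.7% to 58%; nothing in the documents places the trial within that range.

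Two stronger readings are not supported. A reader might infer that false responses pile up at 4 min, but for pure chance the lean is mild (27–30% against 20%), and it concerns first response only, not time to peak. A reader might also infer that the trial's main conclusion is at risk, but the primary analysis, T* and the per-minute responder tests do not use this curve.

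**What to change.** 1. Run the first-response Kaplan–Meier curve in both arms.
2. Define the strata, and name EXP versus CON as the first log-rank and Cox comparison. Any phenotype strata come after it.
3. Report the EXP-minus-CON cumulative first-response proportion at each of the five minutes as the estimate of PAPE onset.
4. Label an EXP-only curve descriptive, and drop the statement that on its own it shows when athletes express PAPE.
5. State the MDC confidence level, and whether it refers to single trials or three-trial means.

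The cost is SAP wording and one further curve. The primary analysis already uses CON jump data at the same five minutes, so no new measurement is needed. The CON curve also shows the actual chance and non-specific rate, whichever MDC is used. The downside is that the reported PAPE response proportion may be lower than the raw EXP curve suggests.

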Moderation and mediation (pre-specified).

All moderators and predictors will be mean-centered; multicollinearity is checked (VIF < 5). Primary moderation models test whether (a) baseline CMJ modifies the effect of %MHC-I on Δ CMJ and (b) baseline morphology (thickness, pennation angle, fascicle length) modifies the effect of baseline CMJ on Δ CMJ. Significant interactions will be decomposed with simple slopes at -1 SD, mean, and +1 SD, with 95% CIs via nonparametric bootstrap (1,000 resamples) and publication-ready interaction plots. Exploratory mediation tests whether acute morphological change (e.g., % Δ thickness at a given minute) transmits baseline morphology effects to % Δ CMJ; indirect, direct, and total effects will be estimated by bootstrap (5,000 resamples; bias-corrected CIs) and interpreted cautiously.

Assumptions, multiplicity, and robustness.

Model diagnostics include residual normality (Shapiro–Wilk), homoscedasticity (residual–fitted patterns, Breusch–Pagan), linearity, and independence by design. Sphericity is tested for rmANOVA (Mauchly) with Greenhouse–Geisser corrections as needed. If mechanistic variables are skewed, appropriate transformations (e.g., log for EMG amplitude) are considered; otherwise we rely on LMM robustness. Multiplicity is controlled via Holm across the five between-group contrasts, FDR for correlation families, and restraint in post-hoc testing; moderation/mediation will be estimation-focused with full interval reporting and are not used to redefine the primary inference.

Reporting, visualization, and software.

We report means \pm SD with 95% CIs; between-group effects as Hedges' g; within-subject effects as d_{nZ} ; ANOVA-style effects as η^2 ; logistic results as ORs with AUC; and survival results as HRs with concordance. Figures include EMM trajectories with 95% CIs, individual waterfall plots with MDC bands, ROC curves for %MHC-I, Kaplan–Meier curves for first/peak response, interaction plots for significant moderations, and path diagrams for supported mediations. Analyses will be performed in Jamovi 2.6 and STATISTICA 13.1.

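### The survival analysis of time to peak and time to first response mixes whether an athlete responds with when, so a phenotype that changes only response size can appear to change timing.

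*Combined protocol and SAP*

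**What the plan says.** All references are to the combined protocol and SAP.

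- **Within-group time-course and kinetics:** for individual timing, "we model time to first and time to peak response (4–12 min) using Kaplan–Meier curves with censoring at 12 min". The analysts will then "compare strata by log-rank tests, and fit Cox proportional-hazards models to estimate hazard ratios (HR, 95% CI) and concordance (C-index"). The section concludes: "This kinetics framework provides an assumption-light estimate of when athletes typically express PAPE". It does not define the peak event, say who is censored, or name the strata or the Cox covariates.
- **Data handling and derived variables:** "Individual response is classified using MDC". No numerical MDC is given.
- **Objectives and endpoints:** measurements are at "post-intervention time points (4, 6, 8, 10, 12 min"). The secondary endpoints link estimated %MHC-I to "the magnitude, timing, and likelihood of response", as three separate properties.
- **Responder analyses and discrimination:** "Responder distributions (Positive/neutral/adverse) will be compared between EXP and CON at each minute". The plan therefore expects some athletes not to respond.
- **Reporting, visualization, and software:** "survival results as HRs with concordance". No summary of timing among responders is listed.

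**The concern.** Censoring means that the event may still occur but has not yet been seen. Time to peak within 4–12 min does not fit that description. Once the 12 min jump is done, the highest of an athlete's five values is known, and an athlete who never exceeded the MDC has no pending peak inside the window. If such athletes are entered as censored at 12 min, the hazard at each minute depends on the share who will ever respond as well as on when responders peak.

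Magnitude and likelihood have their own analyses (Pearson correlations and logistic models). The survival hazard ratio is the only individual-level result on timing, and nothing in it conditions on having responded. A phenotype that only makes the response larger moves more athletes over the MDC and so raises the hazard ratio, which a reader would take as evidence that the phenotype brings the peak forward.

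Time to first response has a related problem. Censoring at the end of follow-up is conventional there, but the hazard ratio still carries both components and cannot be read as timing alone.

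**Working it through.** The plan states no hazard ratio, event count, sample size or MDC value, so there is no figure of its own to reproduce. Three checks were made.

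**1. Exact example.** Inputs: five minutes (from the plan); two strata with the same peak-minute distribution, uniform over the five minutes (assumed); responder probability p = 0.8 and 0.4 (assumed); non-responders censored at 12 min. After the k-th minute, S = 1 − p·k/5. The discrete hazard is (p/5) divided by S at the previous minute.

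| Minute | S, p = 0.8 | S, p = 0.4 | Hazard, 0.8 | Hazard, 0.4 | Ratio |
|---|---|---|---|---|---|
| 4 | 0.84 | 0.92 | 0.160 | 0.080 | 2.0 |
| 6 | 0.68 | 0.84 | 0.190 | 0.087 | 2.2 |
| 8 | 0.52 | 0.76 | 0.235 | 0.095 | 2.5 |
| 10 | 0.36 | 0.68 | 0.308 | 0.105 | 2.9 |
| 12 | 0.20 | 0.60 | 0.444 | 0.118 | 3.8 |

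The median (first S ≤ 0.5) is 10 min against not reached. Among responders the cumulative share is 0.2, 0.4, 0.6 at 4, 6 and 8 min, so the median is 8 min in both strata. The timing difference is entirely a difference in likelihood. The ratio also rises from 2.0 to 3.8, so proportional hazards fails, and Cox needs that assumption.

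**2. Simulation with a size-only phenotype.** There were 600 replicates per setting, two-sided 0.05, Efron ties. The true peak minute was drawn independently of the phenotype. Assumed: MDC 2.0 units, noise SD 0.7, mean amplitude 2.0, phenotype effect 1.0 unit per SD, about 57% responders.

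| EXP n | Time to peak: HR per SD, Cox rejection | First response: HR per SD, Cox rejection | Peak minute, responders only: Cox rejection |
|---|---|---|---|
| 20 | 2.45, 77% | 2.67, 84% | 2.5% |
| 40 | 2.29, 98% | 2.49, 99% | 3.3% |
| 60 | 2.25, 100% | 2.45, 100% | 3.2% |

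With no phenotype effect, time-to-peak rejection is 4–6%. The size depends on the responder rate. At n = 40 the time-to-peak result runs from HR 1.07 with 7% rejection (98% responders, effect 0.5) to HR 3.41 with 97% rejection (29% responders, effect 1.0).

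A second simulation used milder assumptions: error SD 0.7 cm, so MDC95 = 1.96 × √2 × 0.7 = 1.94 cm; mean and SD of gain 1.2 cm; predictor correlated 0.5–0.7 with size; 45–52% responders. Cox rejection for time to peak was 14–33% at n = 15, 22–49% at n = 20 and 35–72% at n = 30. A rank test of peak minute among responders rejected in 5–7%.

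**3. False ever-responders over five looks.** Assume no true effect and independent normal errors of equal variance, with all five changes sharing one baseline. With c = z√2, the probability that at least one change exceeds the MDC is 1 − ∫ φ(b)·Φ(b + c)⁵ db. For z = 1.96 this is 9.1%, and for z = 1.645 it is 16.6%. At a single minute the rates are 2.5% and 5.0%.

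**The case against.** **The peak event is undefined, and one reading is harmless.** If peak means the highest of the five minutes for every athlete, the bias disappears: under the simulation settings tabulated in the working, HR is 1.02–1.03 and rejection 4–6%, with or without censoring peaks that fall at 12 min. This stands as a limit. However, the plan states a censoring rule, applies one phrase to both first and peak response, and defines response by MDC. Under the harmless reading the rule would have little purpose.

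**A reader might infer that the phenotype will be reported as affecting timing.** The documents support only that it can be. The kinetics section does not name %MHC-I as stratum or covariate; that is inferred from the endpoint list. The bias also fades as the responder rate rises.

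**A reader might infer that pure noise gives a plausible mid-window Kaplan–Meier median of 8 min.** That needs the highest-minute-for-everyone reading. Under the reading that produces the bias, pure noise leaves about 91% (MDC95) or 83% (MDC90) censored, and the median is not reached.

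**The plan has other timing evidence and a control comparison.** It locates the within-EXP peak by repeated-measures ANOVA, finds the minute of largest between-group difference, and correlates %MHC-I with change at each minute. The per-minute responder comparison shows the control group's false-responder rate at single minutes. All of this stands. What is missing is an individual timing result free of likelihood, and the cumulative control rate.

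**Ties are a minor matter.** Efron handling was used in the simulations, so the criticism does not rest on them.

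**Conclusion.** The concern holds in a limited form. On the natural reading of the censoring rule, the hazard ratios for time to peak and time to first response mix likelihood with timing and should not be read as timing effects. The exact example establishes this without simulation and shows that proportional hazards need not hold, so *assumption-light* is not an accurate description.

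The mechanism follows from the plan's wording. Its size does not: sample size, MDC value, responder rate and Cox covariates are all assumed. The simulations range from negligible bias when nearly all athletes respond to near-certain false timing results in the larger groups when little more than half do. First response was slightly more affected than peak in the tabulated simulation.

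This is a secondary analysis. A reader might infer that the main result is in doubt; it is not, because the primary repeated-measures ANOVA does not use these outcomes.

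**What to change.** 1. Define the response event, the peak and the ever-responder in the SAP.
2. Drop Kaplan–Meier, log-rank and Cox for time to peak.
3. Analyse whether an athlete responds by logistic regression of ever-responder status.
4. Analyse when as the peak minute among responders, as an ordinal outcome: a rank correlation with %MHC-I, with a proportional-odds fit only if responder numbers allow. Show the control group's distribution beside it.
5. Treat the first-response minute among responders in the same way, but give the peak minute more weight as evidence on timing. A higher curve of identical shape can cross a fixed threshold sooner, so the crossing minute keeps some dependence on size even among responders.
6. If a cumulative first-response curve is kept, show EXP and CON together, because five looks raise the false ever-responder rate to about 9% (MDC95) or 17% (MDC90). Describe any hazard ratio as a combined likelihood-and-timing effect. A discrete-time complementary log-log model would not avoid this, since never-responders stay censored in it.
7. Delete *assumption-light*.

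The change needs SAP wording and a simpler analysis of the same data. The cost is wider intervals, because timing results rest on responders only.

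### A single Cox hazard ratio, with no proportional-hazards check, can understate a shift in response timing with %MHC-I when many athletes never respond (minor, secondary endpoint)

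*Combined protocol and SAP*

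**What the plan says.** The section Objectives and endpoints lists, among the secondary endpoints, associations of neuromuscular phenotype, "estimated as %MHC-I from tensiomyography (TMG)—and the magnitude, timing, and likelihood of response". Timing therefore stands as a target separate from likelihood.

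The section Within-group time-course and kinetics says "we model time to first and time to peak response (4–12 min) using Kaplan–Meier curves with censoring at 12 min". It will then "compare strata by log-rank tests" and "fit Cox proportional-hazards models to estimate hazard ratios (HR, 95% CI) and concordance (C-index". Neither the strata nor the Cox covariate is named. The paragraph closes by describing this framework as resting on few assumptions.

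An event can fall only at the five "post-intervention time points (4, 6, 8, 10, 12 min". Response is classified by the MDC (Data handling and derived variables), whose value is not given.

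In Assumptions, multiplicity, and robustness, the diagnostics are residual normality, homoscedasticity, "linearity, and independence by design", plus sphericity for the repeated-measures ANOVA. Proportional hazards is not among them. Reporting, visualization, and software gives "survival results as HRs with concordance".

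Two other planned analyses bear on the question: logistic models of response on %MHC-I at specific minutes, and Pearson correlations of %MHC-I with ΔCMJ at each minute, with FDR control across correlation families.

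**The concern.** A Cox model with one coefficient assumes that the covariate multiplies the hazard by the same factor at every minute. A pure shift in timing breaks that assumption. Athletes whose phenotype favours an early response have the higher hazard at 4 to 6 min. By 10 to 12 min most early-type athletes who were going to respond have done so. Those still at risk are largely non-responders, and the late types have the higher hazard. One ratio averages the two, and a log-rank test weighs the same opposing differences.

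At stake is how a secondary result is read. An HR near 1 could be reported as no association between phenotype and timing when the effect is real but reverses over the window. Nothing planned would alert the analyst to this, because proportionality is never checked.

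**Working it through.** The documents give no N, MDC value, response share, expected shift or HR, so there is no stated figure to reproduce. Every input below except the five time points is an assumption, and the tests are two-sided at an assumed 5%.

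**1. Does the hazard ratio cross 1?** Take two phenotype strata with the same cumulative response p by 12 min. Among responders, response time is a discretised normal (SD 2 min) on 4, 6, 8, 10, 12, centred at 7 min (early) or 9 min (late). The hazard at t is P(respond at t) / P(not yet responded before t).

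Example, p = 0.4, early stratum. The weights exp(−(t − 7)²/8) are 0.325, 0.882, 0.882, 0.325, 0.044 and sum to 2.458. The response probability at 4 min is 0.4 × 0.325/2.458 = 0.053, and at 6 min 0.4 × 0.882/2.458 = 0.144. The 6-min hazard is 0.144/(1 − 0.053) = 0.152. The late stratum's 6-min hazard is 0.053, so the ratio is 2.85.

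| p | HR, early v late, at 4 / 6 / 8 / 10 / 12 min |
|---|---|
| 0.4 | 7.39 / 2.85 / 1.17 / 0.44 / 0.15 |
| 0.8 | 7.39 / 3.00 / 1.45 / 0.68 / 0.19 |
| 1.0 | 7.39 / 3.08 / 1.67 / 1.20 / 1.00 |

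The ratio crosses 1 when some athletes never respond. When all respond it is still non-proportional but does not cross.

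**2. Power for time to first response.** Assumptions: error SD of a three-trial block 1, baseline included; MDC = 1.96 × √2 × 1 = 2.77; bell-shaped gain over time (SD 2.5 min); the same peak gain for every athlete; peak at 8 min + 1.5 min per SD of %MHC-I.

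At peak gain 3, about 69% respond in both phenotype halves, with mean first response 5.9 v 8.0 min. The HR per SD of %MHC-I is 0.39, 0.55, 1.03, 2.08 and 4.35 at 4, 6, 8, 10 and 12 min. The single Cox HR is 0.82.

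| Peak gain | Single-HR Cox test, n = 20/30/40 | Cox plus %MHC-I × minute, joint 2 df |
|---|---|---|
| 3 | 0.17 / 0.21 / 0.20 | 0.46 / 0.70 / 0.82 |
| 4 | 0.45 / 0.58 / 0.68 | 0.72 / 0.90 / 0.96 |
| 5 | 0.80 / 0.91 / 0.95 | 0.87 / 0.97 / 1.00 |
| 6 | 0.93 / 1.00 / 1.00 | 0.93 / 1.00 / 1.00 |

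Repeat simulations at gain 3 gave 0.15–0.17, 0.18–0.21 and 0.20–0.22 for Cox, so the dip from n = 30 to 40 is simulation error. Null rejection was near 5% for both tests. At gains 5 to 6, 97–100% respond.

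**3. A different event model.** With response times drawn as in step 1, but a continuous covariate, n = 40 and a shift of 2 min per SD, Cox power is 0.08 / 0.17 / 0.48 / 1.00 at cumulative response 0.4 / 0.6 / 0.8 / 1.0. The 2-df test gives 0.63 / 0.85 / 0.97 / 1.00.

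**4. Phenotype also changes likelihood.** With n = 40, shifts of 1–2 min per SD, response 0.4–0.8 and a log odds ratio of 0.7 per SD, Cox gives 0.59–0.90 against 0.61–0.98 if the earlier phenotype responds more often. If it responds less often, Cox gives 0.07–0.39 against 0.60–0.97.

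**5. Time to peak, gain 3, n = 20/30/40.** If every athlete has a peak minute and nobody is censored, Cox gives 0.93 / 0.98 / 1.00 against 0.90 / 0.97 / 1.00 for the 2-df test. If non-responders are censored, Cox gives 0.20 / 0.24 / 0.26.

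**6. Planned per-minute correlations, same scenario as the gain 3 row.** The chance of at least one FDR-significant r is 0.77 / 0.96 / 1.00 (null 0.04).

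**The case against.** The strongest reply is that the plan does not rest on the Cox model alone. The per-minute correlations would show a timing shift as r changing sign from early to late minutes, and in the simulated scenario they detect an association more often than the 2-df hazard test does. The minute-specific logistic models could show it too. A reader might infer that the plan would miss a real timing effect altogether; the documents do not support that. What remains is narrower. Those analyses address size and status at separate minutes and do not formally test whether the association changes over time, so a null HR could still be reported as the timing result and conflict with them.

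The simulations can also be called favourable to the point: gain 3 sits barely above the MDC of 2.77, with no phenotype effect on response size. This stands. With larger gains, or when the earlier phenotype also responds more often, Cox keeps much or all of its power. The result for time to peak depends on whether non-responders are censored, which the plan leaves open.

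Finally, %MHC-I as the covariate is inferred, and the kinetics paragraph has a descriptive aim. That is fair. But %MHC-I is the phenotype measure named for the timing endpoint, and leaving the covariate unnamed is itself a gap.

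**Conclusion.** The point holds conditionally and is minor. Timing is a declared secondary target, the individual-level timing model assumes a constant HR, and no check of that assumption is planned. For time to first response, the single-HR test can have power of about 0.2 where a 2-df test has 0.46 to 0.82 (n = 20 to 40, 69% responding). Two conditions are needed: a material share of athletes who never exceed the MDC by 12 min, and a phenotype effect on when rather than whether they respond. The plan's neutral and adverse response classes and its censoring at 12 min make non-responders plausible, but no share is given.

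Two stronger readings are tempting. One is that a timing effect necessarily makes the HR cross 1; with full response it does not. The other is that the single HR should be replaced and a 2-df test made the only phenotype test. That is a trade-off, because the joint test loses power if phenotype affects only response size. The primary ANOVA is unaffected.

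**What to change.** In Within-group time-course and kinetics:

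- Name %MHC-I as the Cox covariate.
- Keep the overall HR, and prespecify a %MHC-I × minute term (minute centred at 8) as both the proportionality check and the timing test.
- Where that term indicates non-proportionality, report the %MHC-I HR by minute, or early v late, with 95% CIs.
- State that a null single HR, log-rank test or C-index will not be read as absence of a timing effect, and that the result will be interpreted alongside the per-minute correlations.

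Add the check to the diagnostics in Assumptions, multiplicity, and robustness.

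The cost is one model term and a few sentences. Minute-specific HRs will be imprecise in a small sample, and a non-significant interaction will not prove proportionality. The power figures above are for the joint 2-df test; power of the interaction term alone was not calculated. If the joint test is used and phenotype affects only response size, the loss is about 4 to 12 percentage points (for example 0.50 to 0.42, or 0.87 to 0.81, at n = 30).
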